12.5. Appendix 5: Female Eligibility Criteria

A female subject is eligible to participate if she is not pregnant (as confirmed by a negative urine hCG test for females of reproductive potential only), not breastfeeding, or at least one of the following conditions applies:

- Reproductive potential and agrees to follow one of the options listed in the Modified List of Highly Effective Methods for Avoiding Pregnancy in FRP **from 30 days prior to the first dose of randomized treatment and until completion of the Follow-up visit (4-6 weeks after the end of randomized treatment)**; those who permanently discontinue randomized treatment prior to the end of the study should continue contraceptive methods following the Early Treatment Discontinuation Visit until the final pregnancy test assessment at a subsequent study visit (at least 4 weeks after the end of randomized treatment) as described in the Time and Events Table (Section 7.1).
 1. Contraceptive subdermal implant.
 2. Intrauterine device or intrauterine system.
 3. Combined estrogen and progestogen oral contraceptive [Trussell, 2011].
 4. Injectable progestogen [Trussell, 2011]
 5. Contraceptive vaginal ring [Trussell, 2011]
 6. Percutaneous contraceptive patches [Trussell, 2011]
 7. Male partner sterilization prior to the female subject's entry into the study, and this male is the sole partner for that subject [Trussell, 2011]. The documentation on male sterility can come from the site personnel's: review of subject's medical records, medical examination and/or semen analysis, or medical history interview provided by her or her partner.

These allowed methods of contraception are only effective when used consistently, correctly and in accordance with the product label. The investigator is responsible for ensuring that subjects understand how to properly use these methods of contraception.

The list does not apply to FRP with same sex partners or for subjects who are and will continue to be abstinent from penile-vaginal intercourse on a long term and persistent basis, when this is their preferred and usual lifestyle. Periodic abstinence (e.g. calendar, ovulation, symptothermal, post-ovulation methods) and withdrawal are not acceptable methods of contraception.

Note: See Section 12.15.2 for the country-specific requirements for the Czech Republic ONLY relating to acceptable contraceptive methods during participation in this study.

- Non-reproductive potential defined as either:
 1. Pre-menopausal with one of the following: (i) documented tubal ligation; (ii) documented hysteroscopic tubal occlusion procedure with follow-up confirmation of bilateral tubal occlusion; (iii) hysterectomy; or (iv) documented bilateral oophorectomy, or;

2. Postmenopausal defined as 12 months of spontaneous amenorrhea. In questionable cases, a blood sample with simultaneous FSH and estradiol consistent with menopause is confirmatory (FSH ≥ 23.0 MIU/mL (≥ 23.0 IU/L) and estradiol ≤ 10 pg/mL (or ≤ 37 pmol/L) is confirmatory). Females on hormone replacement therapy (HRT) and whose menopausal status is in doubt will be required to use one of the highly effective contraception methods if they wish to continue their HRT during the study. Otherwise, they must discontinue HRT to allow confirmation of post-menopausal status prior to study enrollment.

References

Trussell J, Contraceptive Efficacy. In: Hatcher RA, Trussell J, Nelson AL, Cates W, Kowal D, and Policar M (editors). Contraceptive Technology: Twentieth Revised Edition. New York: Ardent Media, 2011. Table 26-1

12.6. Appendix 6: Randomized Treatment Dose Adjustment Schemes

HemoCue Hgb (g/dL) at current study visit ¹	HemoCue Hgb change since last study visit ¹	Randomized Treatment Dose Adjustment ⁵
<7.5 ²	Any change	Repeat Hgb and average values ⁶ ; if confirmed, increase to the next higher dose step
7.5 to <9.5	Decreasing or No change ⁷	Increase to the next higher dose step
7.5 to <9.5	Increasing ⁸	Maintain dose
≥9.5 to <10 at two consecutive visits	Decreasing or No change	Increase to the next higher dose step
≥9.5 to ≤11.5	Any change	Maintain dose
>11 to ≤11.5 at two consecutive visits	Increasing or No change	Decrease to the next lower dose step
>11.5 to <12	Decreasing	Maintain dose
>11.5 to <12	Increasing or No change	Decrease to the next lower dose step
≥12 ³	Any change	Repeat Hgb and average values ⁶ ; if confirmed, temporary hold the dose and re-check Hgb at next study visit ¹ ; restart at one dose step lower when Hgb <11.5 g/dL and provided it has been at least 2 weeks from the prior study visit
Any	>2 g/dL increase over 4 weeks (>1 g/dL increase over 2 weeks ⁴)	Repeat Hgb and average values ⁶ ; if confirmed, decrease to the next lower dose step
Any	>2 g/dL decrease over 4 weeks (>1 g/dL decrease over 2 weeks ⁴)	Repeat Hgb and average values ⁶ ; if confirmed, increase to the next higher dose step

1. "Study visit" refers to mandated study visits (every 4 weeks through Week 52; then every 12 weeks). From Week 52 onwards, additional study visits to check Hgb and dispense randomized treatment (where directed by the IRT system) are required under the following circumstances (additional visits have a visit window of ±1 week):
 - When Hgb at study visit is outside of the target range, i.e., <10 or >11 g/dL: Visit 4 weeks later to assess for dose adjustment.
 - When the dose of randomized treatment is changed or restarted: Visits every 4 weeks for 12 weeks.
 - When a medication that is a moderate CYP2C8 inhibitor (i.e., clopidogrel, teriflunomide, deferiasirox) is started, stopped, or the dose is changed: Visits every 4 weeks for 12 weeks.
 - When the investigator determines it clinically necessary to evaluate a subject sooner than 12 weeks later: Visit 4 weeks later to assess for dose adjustment.
 - For subjects transitioning to dialysis: Visits every 4 weeks for 12 weeks.
 - For subjects changing dialysis modality from HD to PD: Visits every 4 weeks for 12 weeks.
2. This rule applies to any mandated visit or unscheduled visit, provided it has been at least 2 weeks from the prior study visit.
3. This rule applies to any mandated or unscheduled visit.
4. This rule applies to Week 2 and Week 4 visits only.
5. Those receiving the highest dose of randomized treatment who require a dose increase will maintain the same dose, while those receiving the lowest dose of randomized treatment that require a dose decrease will have doses withheld.
6. Repeat HemoCue Hgb at the same study visit to confirm Hgb (using the same sample) and take average.
7. No change may be redefined as an increase of <0.5 g/dL based on the review of blinded instream aggregate Hgb data.
8. Increasing may be redefined as an increase of ≥0.5 g/dL based on the review of blinded instream aggregate Hgb data.

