6.3.3. Daprodustat and Darbepoetin Alfa Dose Adjustment Algorithm

The protocol-specified randomized treatment (daprodustat or darbepoetin alfa) dose adjustment algorithm is provided in [Appendix 6](#). Dose adjustments (i.e., increase, decrease, maintain, or withheld if ≥ 12 g/dL) will be made programmatically for both the daprodustat and darbepoetin alfa arms by the IRT system to maintain Hgb concentrations within the range of 10-11 g/dL based on the HemoCue Hgb value measured at least every 4 weeks (Day 1 through Week 52) or at least every 12 weeks (post-Week 52 through end of treatment) disclosed to the IRT system by the investigator.

From Week 52 onwards, additional study visits to check Hgb and dispense randomized treatment (where directed by the IRT system) will be required under the circumstances outlined in [Appendix 6](#).

In order to mitigate subjects remaining below the Hgb target range for an extended period of time, adjustments to the algorithm may be implemented by the sponsor as outlined in [Appendix 6](#) based on the review of blinded instream aggregate Hgb data.

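### Appendix 6 gives conflicting dose instructions, with no stated precedence, to a subject held for Hgb ≥12 g/dL whose Hgb is below 11.5 at the re-check after a rapid fall

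*Protocol*

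**What the plan says.** Appendix 6 holds the dose-adjustment table for both arms. Section 6.3.3 says that dose changes "will be made programmatically for both the daprodustat and darbepoetin alfa arms by the IRT system". Two rows of the table matter here.

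- **Hgb ≥12 g/dL, any change.** After confirmation on a repeat reading, the instruction is to "temporary hold the dose and re-check Hgb at next study visit" and then to "restart at one dose step lower when Hgb <11.5 g/dL and provided it has been at least 2 weeks from the prior study visit". Footnote 3 applies this row at any mandated or unscheduled visit.
- **Any current Hgb, rapid fall (last row).** The trigger is ">2 g/dL decrease over 4 weeks", or more than 1 g/dL over 2 weeks, which footnote 4 limits to the Week 2 and Week 4 visits. After a repeat reading, the action is: "if confirmed, increase to the next higher dose step".

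Footnote 1 sets study visits 4 weeks apart through Week 52 and 12 weeks apart afterwards. It adds extra visits after Week 52: "When Hgb at study visit is outside of the target range, i.e., <10 or >11 g/dL: Visit 4 weeks later to assess for dose adjustment". Under footnote 5, a subject at the top dose who needs an increase stays at that dose, and a subject at the lowest dose who needs a decrease has doses withheld.

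**The concern.** The rapid-fall row makes no exception for a subject whose dose is on hold, and stopping treatment is one obvious reason for Hgb to fall. One row therefore sends such a subject back to treatment below the previous dose, while the other raises the dose. The table is the published source for an automated dosing rule in both arms. If its rows conflict, the protocol does not determine which dose the subject receives, and a reader cannot check the IRT against it. The exploratory endpoints in Appendix 2 on Hgb of 12 g/dL or more, time on hold and number of dose adjustments all describe how this algorithm behaves.

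**Working it through.** The plan states no figure to reproduce. The check is whether the two conditions overlap, and what the instructions are where they do.

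**1. Timing.** The re-check after a hold is at the next study visit, 4 weeks later through Week 52. After Week 52, a value of 12 or more lies above 11 g/dL, so footnote 1 again brings the subject back at 4 weeks. The re-check interval therefore normally matches the 4-week window of the rapid-fall row, and the 2-week minimum for restarting is met.

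**2. Overlap, 4-week criterion.** Let h be the Hgb at the hold (h ≥ 12.0) and x the Hgb at the re-check. The rapid-fall row needs h − x > 2.0, so x < h − 2.0. The restart clause needs x < 11.5. If h ≤ 13.5, then x < 13.5 − 2.0 = 11.5. Every qualifying fall from a hold value of 12.0 to 13.5 therefore meets both rows. Examples are 12.3 to 10.0 (fall 2.3) and 13.0 to 10.8 (fall 2.2). Only above 13.5 can a qualifying fall leave Hgb at 11.5 or more, where the restart clause is not yet met.

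**3. Overlap, 2-week criterion.** For a hold at Week 2 and a re-check at Week 4, the row needs h − x > 1.0. If h ≤ 12.5, then x < 11.5 and both rows are met, as in 12.3 to 11.2 (fall 1.1).

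**4. What the 4-week criterion does outside a hold.**

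- Below 9.5 with Hgb falling, other rows already increase the dose.
- At a current Hgb of 10 or more, a fall of more than 2 means the previous value exceeded 10 + 2 = 12. If that value was confirmed, the dose was already held.
- What remains is a current Hgb of 9.5 to below 10, from a previous value above 11.5 and below 12.

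Most of the range in which this criterion changes anything is therefore the range in which it meets the hold rule.

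**5. Distance between the instructions.** The darbepoetin steps in Table 5 are 20, 30, 40, 60, 80, 100, 150, 200, 300 and 400 µg per 4 weeks. The protocol does not say from which dose the increase is counted during a hold.

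| Pre-hold dose (µg) | Restart lower | Increase counted from pre-hold dose | Increase counted from reduced dose |
|---|---|---|---|
| 40 | 30 | 60 | 40 |
| 150 | 100 | 200 | 150 |
| 400 (top) | 300 | 400, unchanged (footnote 5) | 400 |

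From 150 µg the gap is two steps (200/100 = 2.0-fold) on one reading and one step (150/100 = 1.5-fold) on the other. At the top dose the instructions differ by one step on either reading.

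**6. Search for a tie-breaker.** Footnotes 1 to 8 of Appendix 6 and Sections 4.4.2, 6.3.1 to 6.3.5 and 6.12 give no order of precedence between these two rows.

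**The case against.** The strongest reply is that the ≥12 row describes a complete sequence of hold, re-check and restart. It is the only row written for a subject with no active dose, so the specific rule should displace the general ones. If the ordinary rows did apply during a hold, the row that maintains the dose between 9.5 and 11.5 would also clash with most restarts. This reading is plausible, but the protocol does not state it. A blanket rule does not supply it either. If rows with an Hgb band always outrank those for any Hgb, the 4-week fall criterion never has an effect. If the rows for any Hgb always win, a subject still at 12 or more would be told to increase.

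A second reply is that the IRT, not the site, applies the table, and may already contain a precedence used identically in both arms. That may be so. The IRT specification is not part of the protocol, and the protocol cannot serve as its reference while its rows conflict.

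A reader might also infer more than the document supports:

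- **A conflict while Hgb is still 12 or more (14.6 to 12.4, say).** Section 6.3.3 lists withholding at ≥12 without qualification, footnote 3 applies it at every visit, and the transfusion text in Section 6.12 lets the hold override a maintain instruction. These point to the hold governing there.
- **That large falls are common on hold.** Take the red-cell lifespan of almost 3 months in Section 4.4.1 as 13 weeks and assume linear loss. A fall from 13 in 4 weeks is then 13 × 4/13 = 4.0 g/dL with no red-cell production at all. It is (13 − 8) × 4/13 = 1.5 or (13 − 9) × 4/13 = 1.2 if production off drug sustains 8 or 9 g/dL. The range spans the 2 g/dL trigger, so it does not establish frequency.
- **That Appendix 4 singles out subjects just above 12.** It refers to Hgb above the upper limit of normal in animals and, for phase 2, to Hgb above 13.5 or a rise of more than 1 g/dL in 2 weeks.
- **An effect on MACE or the Hgb co-primary.** None is shown. The same table runs in both arms, and Section 9.2.2 puts power for Hgb non-inferiority above 99%.

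**Conclusion.** The contradiction holds for a subject on hold whose re-check Hgb is below 11.5 after a confirmed fall of more than 2 g/dL over 4 weeks, or more than 1 g/dL over 2 weeks between Weeks 2 and 4. That subject meets two rows with conflicting instructions and no stated precedence. The overlap is complete for hold values up to 13.5 g/dL (4-week criterion) or 12.5 g/dL (2-week criterion), assuming the re-check takes place on schedule. The size in dose terms rests on an unstated reference dose: two steps or one, and at the top dose a one-step decrease against no change. A twofold dose difference is therefore one reading and not a fact of the protocol. The number of subjects affected cannot be derived. This is an inconsistency in the dosing specification that should be corrected; it is not evidence of bias in either co-primary comparison.

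**What to change.** Reconcile the ≥12 hold-and-restart row with the rapid-fall row. Add a footnote to Appendix 6 stating which row governs for a subject on hold, and from which dose any step is counted. The same footnote can settle how the maintain row for 9.5 to 11.5 relates to a held subject. Then verify that the IRT logic matches the text in both arms; if the IRT already contains a precedence, the footnote should record it once the clinical team has confirmed it. Which instruction should govern is for the sponsor's clinical team, and none is proposed here. The cost is one footnote and a check of the IRT specification, with no new data and no change to the analysis.

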12.7. Appendix 7: Time and Events Table for Subjects Transitioning to Dialysis

Table 12 Schedule of Assessments Year 1 to the End of the Study for Subjects Transitioning to Dialysis

Protocol activity (visits ± 1 week, except Weeks 2 and 4 which are ± 3 days) All assessments pre-dialysis unless otherwise specified (Note: All visit timings are relative to Day 1)	Day 1 through Week 52				
	Week 2	Full study visit Week 4, 16, 28, 40	Abbreviated study visit Week 8, 12, 20, 24, 32, 36, 44, 48	Week 52	Unscheduled ⁸
IRT system transaction	X	X	X	X	X
Subject reminder, inform site staff of changes in health ¹				X	
Weight (pre- and post-dialysis for in-center HD subjects (when possible); between treatments for HHD; at study visits as per standard of care for PD) and EDW	X	X	X	X	X
SBP/DBP, HR (pre- and post-dialysis for in-center HD subjects (when possible); between treatments for HHD; as per standard of care for PD) (single readings unless otherwise indicated)	X	X	X	X (triplicate)	X
Kt/V _{urea} ¹⁴		X		X	
ECG ²				X	
Randomized treatment dispensing (start administration on day of dispensing) ¹⁶	X ¹⁵	X	X	X	X ^{9,15}
Randomized treatment compliance ¹⁶	X ⁹	X	X	X	X ⁹
Iron therapy, transfusions ³	X	X	X	X	X
Rescue medication ^{3,4}		X	X	X	
FRP only: Serum pregnancy test ^{5,17}		X		X	
HemoCue Hgb	X	X	X	X	X
Hematology ⁶		X	Hgb only	X	X
Clinical chemistry ⁶		X		X	X
Ferritin, total iron, UIBC ⁶		X		X	
Hepcidin		X		X	
HbA1c ⁷ , lipids (non-fasting)				X	
hsCRP, iPTH		Wk 28		X	
Storage biomarkers ¹³		Wk 28		X	
Hospitalization ³ , kidney transplant ³	X	X	X	X	X
Non-serious AEs, SAEs, AEs of special interest, clinical events	X	X	X	X	X
Review concomitant medications	X	X	X	X	X

Table 12 Schedule of Assessments Year 1 to the End of the Study for Subjects Transitioning to Dialysis (continued...)

Protocol activity (visits ± 1 week) All assessments pre-dialysis unless otherwise specified (Note: All visit timings are relative to Day 1)	Year 2				Year 3				Year 4					Unscheduled ^{8,10}	End of Study ¹⁴	Follow-up (4-6 weeks after stopping randomized treatment)	
	Week 64	Week 76	Week 88	Week 100	Week 112	Week 124	Week 136	Week 148	Week 160	Week 172	Week 184	Week 196	Week 208 ¹¹				
IRT system transaction	X	X	X	X	X	X	X	X	X	X	X	X	X	X	X	X	X
Weight (pre- and post-dialysis for in-center HD subjects (when possible); between treatments for HHD; at study visits as per standard of care for PD) and EDW	X	X	X	X	X	X	X	X	X	X	X	X	X	X	X	X	X
SBP/DBP, HR (pre- and post-dialysis for in-center HD subjects (when possible); between treatments for HHD; at study visits as per standard of care for PD) (single readings unless otherwise indicated)	X	X	X	X	X	X	X	X	X	X	X	X	X	X	X	X	X (triplicate)
Kt/V _{urea} ¹⁴	X		X		X		X		X		X		X				
ECG ²				X				X					X				
Randomized treatment dispensing (start administration on day of dispensing) ¹⁶	X	X	X	X	X	X	X	X	X	X	X	X	X	X	X ¹⁵		
Randomized treatment compliance ¹⁶	X	X	X	X	X	X	X	X	X	X	X	X	X	X	X ⁹	X	
Iron therapy, transfusions ³	X	X	X	X	X	X	X	X	X	X	X	X	X	X	X	X	
Rescue medication ^{3,4}	X	X	X	X	X	X	X	X	X	X	X	X	X	X			
FRP only: serum pregnancy test ^{5,17}	X	X	X	X	X	X	X	X	X	X	X	X	X	X		X	X
HemoCue Hgb	X	X	X	X	X	X	X	X	X	X	X	X	X	X	X		
Hematology ⁶	X	Hgb only	X	Hgb only	X	Hgb only	X	Hgb only	X	Hgb only	X	Hgb only	X	X	X	X	X
Clinical chemistry ⁶	X		X		X		X		X		X		X	X	X	X	X
Ferritin, total iron, UIBC ⁶	X	X	X	X	X	X	X	X	X	X	X	X	X	X		X	X
Hepcidin, HbA1c ⁷ , lipids (non-fasting), hsCRP				X													

Protocol activity (visits ±1 week) All assessments pre-dialysis unless otherwise specified (Note: All visit timings are relative to Day 1)	Year 2				Year 3				Year 4					Unscheduled ^{8,10}	End of Study ¹⁴	Follow-up (4-6 weeks after stopping randomized treatment)
	Week 64	Week 76	Week 88	Week 100	Week 112	Week 124	Week 136	Week 148	Week 160	Week 172	Week 184	Week 196	Week 208 ¹¹			
iPTH		X		X												
Hospitalization ³ , kidney transplant ³	X	X	X	X	X	X	X	X	X	X	X	X	X	X	X	X
Non-serious AEs, SAEs, AEs of special interest, clinical events	X	X	X	X	X	X	X	X	X	X	X	X	X	X	X	X
Review concomitant medications	X	X	X	X	X	X	X	X	X	X	X	X	X	X	X	X

- Health changes include new symptoms or medical problems (e.g., pregnancy, hospitalizations) and changes in medication
- ECG assessments may be recorded pre or post dialysis.
- Record in eCRF, if applicable.
- See details on Rescue in Section 6.12.
- Repeat pregnancy test prior to placebo run in or randomized treatment re-administration if it is disrupted for >7 days and there was also a lapse in contraceptive use, regardless of the reason for the disruption. If a subject becomes post menopausal (as defined in Appendix 6) during the study pregnancy tests are no longer required.
- See details on hematology and clinical chemistry in Section 7.4.11
- HbA1c assessment only in subjects with diabetes on Day 1 or diagnosed during the study.
- If a subject lost their placebo run-in or randomized treatment, it is not necessary to perform the unscheduled visit assessments other than dispensing placebo run-in or randomized treatment.
- Required only if dose is changed or randomized treatment is dispensed.
- Additional visits to check Hgb and dispense randomized treatment are required under the circumstances described in Appendix 6. Hematology and chemistry samples are not required. For any unscheduled visit, compliance checking will be required when a dose of randomized treatment is changed.
- Further visits every 12 weeks as required.
- Investigator will inform subject when to attend this End of Study visit (Section 6.3.4).
- Biomarker samples will be stored for future analyses for all subjects, except if not permitted by IRB/EC or refused by subject.
- A historical Kt/Vurea measurement can be used. If a Kt/Vurea measurement is not available, then a urea reduction ratio measurement is acceptable. Kt/Vurea and urea reduction ratio measurements are not required for daily HHD.
- If dose does not change, then randomized treatment is returned to subject.
- In circumstances where the new dose of randomized treatment cannot be dispensed on the day of the study visit, the new dose of randomized treatment can be dispensed at next HD treatment. Prior randomized treatment should be continued unless on dose hold, Hgb ≥ 12 g/dL. Compliance is deferred until randomized treatment is returned.
- For Argentina ONLY:** Pregnancy testing will be performed every 4 weeks for FRP as required by local law.

For schedule of assessments for patient reported outcomes, genetics and sub-studies refer to Table 8 in the main body of the protocol. For schedule of assessments for subjects permanently discontinuing randomized treatment refer to Table 9 in the main body of the protocol.

12.8. Appendix 8: Definition of and Procedures for Recording, Evaluating, Follow-Up and Reporting of Adverse Events

Adverse Event Definition:

- An AE is any untoward medical occurrence in a patient or clinical investigation subject, temporally associated with the use of a medicinal product, whether or not considered related to the medicinal product.
- NOTE: An AE can therefore be any unfavorable and unintended sign (including an abnormal laboratory finding), symptom, or disease (new or exacerbated) temporally associated with the use of a medicinal product.

Events meeting AE definition include:

- Any abnormal laboratory test results (hematology, clinical chemistry, or urinalysis) or other safety assessments (e.g., ECGs, radiological scans, SBP, DBP or HR measurements), including those that worsen from baseline, and felt to be clinically significant in the medical and scientific judgment of the investigator.
- Exacerbation of a chronic or intermittent pre-existing condition including either an increase in frequency and/or intensity of the condition.
- New conditions detected or diagnosed after placebo run-in or randomized treatment administration even though it may have been present prior to the start of the study.
- Signs, symptoms, or the clinical sequelae of a suspected interaction.
- Signs, symptoms, or the clinical sequelae of a suspected overdose of either placebo run-in, randomized treatment or a concomitant medication (overdose per se will not be reported as an AE/SAE unless this is an intentional overdose taken with possible suicidal/self-harming intent. This should be reported regardless of sequelae).
- "Lack of efficacy" or "failure of expected pharmacological action" per se will not be reported as an AE or SAE. However, the signs and symptoms and/or clinical sequelae resulting from lack of efficacy will be reported if they fulfill the definition of an AE or SAE.

Events NOT meeting definition of an AE include:

- Any clinically significant abnormal laboratory findings or other abnormal safety assessments which are associated with the underlying disease, unless judged by the investigator to be more severe than expected for the subject's condition.
- The disease/disorder being studied or expected progression, signs, or symptoms of the disease/disorder being studied, unless more severe than expected for the subject's condition.

- Medical or surgical procedure (e.g., endoscopy, appendectomy): the condition that leads to the procedure is an AE.
- Situations where an untoward medical occurrence did not occur (social and/or convenience admission to a hospital).
- Anticipated day-to-day fluctuations of pre-existing disease(s) or condition(s) present or detected at the start of the study that do not worsen.

